TITLE: PET MYOCARDIAL BLOOD FLOW COMPARISON TO CORONARY CTA and CT-FFR

INVESTIGATORS: [name].
[name].
[name].
[name].
[name].
[name].

Cardiovascular Imaging Laboratory, Washington University School of Medicine, St. Louis, MO, [contact], [contact], [contact]

I. **Rationale:** Ischemic heart disease is a major public health problem. Twenty-five percent of men and seventeen percent of women between the ages of 60 to 79 have coronary artery disease (CAD) and these figures increase with age. Ischemic heart disease is also the number one cause of death in men and women (1). A variety of non-invasive testing has been developed to evaluate for CAD in an attempt to guide treatment and revascularization planning. Approaches include both anatomic evaluation of the coronary arteries as well as functional evaluation of the myocardium for ischemia. Modern CT scanners have allowed for coronary CT angiography (cCTA) to provide a reliable anatomic evaluation of coronary vessel patency and a very high negative predictive value for CAD. However, anatomic determination of stenotic degree alone has not proven to be a reliable surrogate for hemodynamic significance. More recently, the development of cCTA fractional flow reserve (cCTA-FFR) has transformed the evaluation from being a solely anatomical study to one that also provides functional hemodynamic data. Still, while the validity of this noninvasive hemodynamic data has been verified in numerous prospective studies at this point, the utility of cCTA-FFR remains limited in most institutions. This has largely been due to the exceptional computations required to create the FFR data and the reliance on a single company (HeartFlow) to provide the computing offsite which can lead to delays in obtaining results. As a different approach to assess CAD, PET myocardial blood flow (MBF) and myocardial perfusion reserve (MPR) have shown great sensitivity in determining both regional and global ischemia. However, the lack of coronary anatomic information hinders the specificity of these methods. Interestingly, Kajander et al have shown the superiority of a hybrid approach (combining PET-cCTA) when compared to either modality alone (2). Modern imaging systems allow this model to be taken one step further, combining PET with cCTA and CT-FFR. Furthermore, at-workstation models of calculating FFR data could help to bring this technique into much wider usage.

We propose to perform a pilot study which will compare N-13 ammonia PET regional MBF and MPR to the presence to coronary artery stenoses on cCTA and their significance by CT-FFR. PET MBF/MPR and CT-FFR will then be compared to the reference standard of invasive coronary catheterization (ICA) with invasive FFR measurements.

II. Objective:

The broad, long-term objective of this pilot study is to develop an optimal, clinically usable, non-invasive evaluation of CAD in the setting of stable angina which provides both anatomic and functional information.

In this study our primary endpoint is significant stenosis for flow limiting lesions (≤ 0.8) by CT-FFR. We will derive sensitivity, specificity, NPV, PPV of CTA-cFFR compared to the reference standard of standard of care ICA with FFR for each epicardial coronary artery.

Our secondary endpoint will be the correlation of segmental PET MBF and MPR to presence or absence of a coronary artery stenosis $\geq 50\%$ diameter, and in patients with stenosis $\geq 50\%$ diameter, correlation with CT-cFFR, and ICA/ICA FFR for which we will perform a Pearson correlation coefficient. We will also compare a hybrid model of PET MPR-CTA-cFFR to standard of care ICA with FFR. We will record patient risk factors. We anticipate that MBF/MPR may not always correlate with anatomic information or FFR, especially in the presence of small vessel disease, and that, in some patients, this information will be complementary.

III. Eligibility Criteria:

Inclusion Criteria:

- 18-90 years of age, of either sex
- Patients presenting with stable angina and a moderate pretest likelihood for CAD and scheduled to undergo ICA for the clinical indication of angina. Subjects will undergo this study within 45 days prior to the cardiac catheterization. This study can also be performed 45 days after the cardiac catheterization if the patient had no interventions.

Exclusion criteria:

- Prior history of stenting, coronary artery bypass graft surgery, or myocardial infarction, unstable angina, atrial fibrillation, second or third degree atrioventricular block, class IV heart failure
- Iodine allergy
- Renal dysfunction (creatinine above normal laboratory limits)
- Symptomatic asthma
- Women who are pregnant or breast-feeding

IV. Methods:

Subjects and Recruitment: This is a single cohort, technology assessment study. Thirty-five patients presenting with stable angina and a moderate pretest likelihood for CAD who are already scheduled to undergo ICA for the clinical indication of angina will be recruited to undergo PET-CTA-cFFR. Exclusion criteria include: Prior history of stenting, coronary artery bypass graft surgery, or myocardial infarction, unstable angina, atrial fibrillation, second or third degree atrioventricular block, class IV heart failure, iodine allergy, renal dysfunction, symptomatic asthma, and pregnancy.

Patient history will be gathered on the following: gender, age, weight, BMI, risk factors (HTN, DM, DLD, smoking), family history, and medications (statins, Beta blockers, Nitrates, ASA).

Recruited patients will undergo cCTA and concurrent N-13 ammonia stress and rest PET evaluation. Patients will undergo their clinically scheduled ICA with FFR within 2 weeks. ICA with FFR will be compared to each of these modalities alone (cCTA, CTA-cFFR, PET MBF/MPR) as well as a hybrid model of these modalities together (PET-cCTA-cFFR). Patients will be contacted by phone 24-72 hours after scanning to ask about any interval changes in health. The coordinator will also call the patient between 25-30 days following their ICA to assess for major adverse cardiovascular event (MACE) defined as hospital readmission for myocardial infarction, angina, or ventricular arrhythmia, or cardiovascular death. The protocol will be reviewed and approved by the Washington University Human Studies Committee and all patients will receive informed consent.

Patients who have already undergone a cCTA within 45 days of their planned PET/CT will not undergo the cCTA component of the research examination. Rather, their cCTA will be collected retrospectively for research evaluation.

V. Imaging Protocol:

Recruited patients will be evaluated on a Siemens Vision PET/CT scanner (128-slice Siemens Edge).

PET-CTA Examination:

If the subject has not had prior cCTA imaging, a comprehensive cardiac PET-cCTA will be performed with acquisition of PET and cCTA imaging in the same setting.

cCTA: The CT portion of the exam will be obtained first. Intravenous esmolol (500 mcg/kg over 1 min and then 100-250 mcg/kg/min) will be administered before the scan to reach a target heart rate of 65 beats per minute. Blood pressure monitoring will occur at each level to ensure systolic blood pressure stays above 100mmHg. Sublingual nitrate (0.4 mg) will be given immediately before the exam.

Scout imaging and non-contrast AC CT scan will be obtained. Then a noncontrast CT coronary calcium (CAC) examination (EKG-gated, sequential) will be performed. Subsequently, iodinated contrast will be infused (100 mL at 4 mL/sec) intravenously followed by a 50 mL saline bolus at the same injection rate and the cCTA performed.

Stress PET: After a 10 minute delay, to allow the heart rate to return to baseline, regadenoson will be hand injected continuously (prefilled syringe: 0.4 mg / 5 mL) over 10 seconds. After an additional interval of 15-20 seconds, 10-12 mCi N-13 ammonia will be hand injected as a bolus followed by immediate injection of 10 mL saline solution over 30 sec. PET emission scan in list mode will be started scan exactly with or seconds before N-13 ammonia injection.

Rest PET: Approximately 30-40 minutes later, to allow sufficient decay of N-13 ammonia to avoid residual activity in the heart, we will perform the rest imaging. A repeat non-contrast AC CT scan will be obtained and the rest PET N-13 ammonia perfusion imaging will be performed. After intravenous injection of \approx 10-12 mCi of N-13 ammonia, PET acquisition over 10 minutes in list mode will be conducted.

If the subject has previously undergone cCTA imaging within 1 month of the scheduled invasive coronary angiogram, the cCTA component of the above examination (to include the CAC) will not be performed.

VI. Image Analysis:

The cCTA will be reviewed by a cardiac CT radiologist ([name]) using a Vital Images workstation for epicardial coronary artery stenoses $\geq 50\%$ diameter. In these lesions $\geq 50\%$ diameter, CT-FFR will be calculated using a computational flow/AI FFR program (Siemens). CAC score will also be obtained using Vital Images software. Segmental MBF at stress and rest, and MPR will be calculated using QPET, Cedar-Sinai software.

VII. Statistical analysis:

Our primary endpoint will be significant stenosis for flow limiting lesions (≤ 0.8) by CT-FFR. We will derive sensitivity, specificity, NPV, PPV of CTA-cFFR compared to the reference standard of ICA with FFR for each epicardial coronary artery.

Our secondary endpoint will be the correlation of segmental PET MBF and MPR to presence or absence of a coronary artery stenosis $\geq 50\%$ diameter, and in patients with stenosis $\geq 50\%$ diameter, correlation with CT-cFFR, and ICA/ICA FFR for which we will perform a Pearson correlation coefficient. We will also compare a hybrid model of PET MPR-CTA-cFFR to ICA with FFR. Spearman's rank correlation coefficient may be used as an alternative if there are issues with the assumption of a linear model. Descriptive statistics will be used to portray demographic and clinical characteristics of study participants and clinical outcomes at 25-30-day follow-up.

CAC in each epicardial artery will be compared to regional MBF.

Sample size justification

The primary aim of this study is to estimate the sensitivity, specificity and other measures of accuracy. As such, the width of the confidence interval around these estimates are important. Based on a study by Driessens et. al, these proportions are expected to be at least 0.75. A sample size of 35 produces a two-sided 95% confidence interval with a width equal to 0.287 or (0.607, 0.893) when the proportion is 0.75. Additionally, a sample size of 35 achieves 80% power to detect a correlation of 0.45 using a two-sided Pearson correlation with a significance level of 0.05.

VIII. Time Line

Patient recruitment/Imaging exams: 4-6 months

Image and data analysis: 1 month

IX. Funding Source: Departmental**X. References**

- 1) Fihn SD et al. 2012 ACCF/AHA/ACP/AATS/PCNA/SCAI/STS guideline for the diagnosis and management of patients with stable ischemic heart disease. *Circulation*. 2012;126:e354-e471.

- 2) Kajander S et al. Cardiac positron emission tomography/computed tomography imaging accurately defects anatomically and functionally significant coronary artery disease. *Circulation.* 2010;122:603-613.
- 3) Driessen RS et al. Comparison of coronary computed tomography angiography, fractional flow reserve, and perfusion imaging for ischemia diagnosis. *J Am Coll Cardiol.* 2019;73:161-73.

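### The only MACE call is timed from ICA, so for patients scanned after ICA part or all of the reported window precedes the scan and is partly immortal time

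*Combined protocol and SAP*

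**What the plan says.** - **Follow-up (Section IV, Subjects and Recruitment).** One MACE assessment applies to all patients: "The coordinator will also call the patient between 25-30 days following their ICA to assess for major adverse cardiovascular event (MACE". MACE is "defined as hospital readmission for myocardial infarction, angina, or ventricular arrhythmia, or cardiovascular death". The only contact timed from the scan is a general health call 24-72 hours afterwards.
- **Order of scan and ICA (Section III, Inclusion Criteria).** The usual order is scan first: "Subjects will undergo this study within 45 days prior to the cardiac catheterization". A second route is allowed: "This study can also be performed 45 days after the cardiac catheterization if the patient had no interventions". No separate follow-up rule is given for this second group.
- **A competing interval (Section IV).** With the scan first, "Patients will undergo their clinically scheduled ICA with FFR within 2 weeks".
- **Exclusions (Section III, repeated in Section IV).** "Prior history of stenting, coronary artery bypass graft surgery, or myocardial infarction, unstable angina, atrial fibrillation", among others. The date on which these are judged is not stated.
- **Use of the data (Section VII).** Descriptive statistics only, for "clinical outcomes at 25-30-day follow-up". Neither the date from which events are counted nor a split by scan order is given.

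**The concern.** The call is tied to one procedure, while the two procedures may come in either order and up to 45 days apart. A patient scanned late after ICA reaches the end of the call window before the study examination takes place. Time between ICA and scan is also conditioned on the patient getting as far as the scan: alive, without an intervention, and possibly without MI or unstable angina. Counting such time as follow-up lowers the apparent event rate in that group.

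At stake is the meaning of the 25-30-day outcome summary. With 35 patients, one or two events placed in or out of the window change the reported proportion visibly: 1/35 = 2.9% and 2/35 = 5.7%.

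**Working it through.** The plan gives no event rate, power or precision figure for MACE, so there is no figure to reproduce. The check is date arithmetic.

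**Inputs.** Call on day c = 25 to 30 after ICA (Section IV). Scan on day s after ICA, s up to 45 (Section III, read as up to day 45). Alternative cap of 14 days if the 2-week interval in Section IV also governed scans after ICA; that sentence describes ICA following the scan, so this is an assumption.

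**Step 1: share of the window before the scan.** Share = min(s, c)/c.

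| Scan day after ICA | Call on day 30 | Call on day 25 |
|---|---|---|
| 5 | 17% | 20% |
| 10 | 33% | 40% |
| 14 | 47% | 56% |
| 20 | 67% | 80% |
| 25 | 83% | 100% |
| 30 or later | 100% | 100% |

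A scan within about 12 days of ICA leaves more than half of the window after the scan. If Section III is read literally as day 45, all of the window precedes the scan.

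**Step 2: averages, assuming scan days spread evenly over 0-45** (the documents give no distribution).

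- Call on day 30: mean days before the scan = 30²/(2 × 45) + 30 × 15/45 = 10 + 10 = 20, and 20/30 = 67%. Scans after the window has closed: 15/45 = 33%.
- Call on day 25: 25²/(2 × 45) + 25 × 20/45 = 6.9 + 11.1 = 18.1, and 18.1/25 = 72%. Scans after the call: 20/45 = 44%.

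**Step 3: the same with a 14-day cap.** The mean scan day is 7. Call on day 30: 7/30 = 23% on average, at most 14/30 = 47%. Call on day 25: 7/25 = 28% on average, at most 14/25 = 56%. No scan then follows the call.

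**Step 4: the whole cohort.** If k of the 35 are scanned after ICA, the share of all 30-day window time before the scan is (k/35) × 67% under the 45-day spread. For assumed k = 1, 5 and 10 this is 1.9%, 9.5% and 19%. With the 14-day cap, k = 5 gives (5/35) × 23% = 3.3%.

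**Step 5: which events the pre-scan days can contain.**

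| MACE component | Possible before the scan in a scanned patient? |
|---|---|
| Cardiovascular death | No |
| Readmission for MI | No, if eligibility is checked at the scan; yes, if checked only before ICA |
| Readmission for angina | Unstable angina: as for MI. Other angina: yes |
| Readmission for ventricular arrhythmia | Yes |

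The pre-scan time is therefore partly, not wholly, immortal.

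**Step 6: post-scan time at the call.** A scan 45 days before ICA gives 45 + 25 = 70 to 45 + 30 = 75 days from scan to call. A scan 45 days after ICA comes 45 − 30 = 15 to 45 − 25 = 20 days after the call, so no post-scan MACE time is collected. The range across one cohort is 0 to 75 days.

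**The case against.** The strongest reply is that the scan need not be the time origin. The call is tied to ICA and the definition speaks of readmission, which fits follow-up after the invasive procedure. MACE is neither a primary nor a secondary endpoint; it is described in a 35-patient pilot, with no test and no prognostic claim. The post-ICA route is an additional one of unknown size, and under a 2-week cap the problem shrinks. All of this stands, and it limits the severity. It does not remove the selection: even with ICA as the intended origin, a patient in the post-ICA group contributes days during which death would have prevented the scan.

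A reader might infer four stronger conclusions that the documents do not support.

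- *The pre-scan days are guaranteed event-free.* Readmission for ventricular arrhythmia, or for angina that is not unstable, is not an exclusion. The MI and unstable angina part depends on an assessment date that is not given. Section IV recruits patients already booked for ICA, which may mean eligibility is judged beforehand; the no-intervention condition can only be checked after ICA, but intervention is not a MACE component.
- *Events between a pre-ICA scan and ICA are lost.* The plan dates the call, not the start of counting, and the call could ask about that period.
- *The call cannot be made for late scans.* It can be made on schedule for anyone recruited before the window closes.
- *Late-scanned patients have no safety contact.* The 24-72 hour call applies whatever the order, and nothing gives the MACE call a safety role for the scan.

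**Conclusion.** The point holds, as a minor one. Followed as written, the plan gives patients scanned after ICA a MACE window that lies partly before the scan, and wholly before it for scans after day 30. For a 30-day window the average pre-scan share is 67% if scan days are even over 0-45, and 23% (maximum 47%) if a 2-week limit applied. Both rest on an assumed even spread and concern only the post-ICA group, whose size is not stated. Those days exclude cardiovascular death by necessity among scanned patients, and MI and unstable angina only if eligibility is checked at the scan. The direction of the effect is a lower apparent MACE rate in that group. The size of that lowering cannot be computed, because no event rate is given. The sensitivity, specificity, predictive value and correlation analyses do not use MACE and are not affected.

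**What to change.** - **Section IV:** time the MACE call 25-30 days after the later of the PET/CT and the ICA.
- **Section VII:** count MACE from that same later date, so that every patient has the same 25-30-day window. Counting from the PET/CT instead would leave 25 to 75 days of unequal follow-up. Report events between scan and ICA separately for patients scanned first, and present the summary by scan order with the number in each group.
- **Sections III and IV:** reconcile the 45-day and 2-week intervals between scan and ICA, since the size of the problem depends on them, and state when the exclusion criteria are assessed.

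The cost is protocol wording and a later telephone call for patients scanned after ICA, up to 45 + 30 = 75 days after their ICA. No extra patients, visits or scans are needed.

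### The 30-40 minute gap between stress and rest PET does not by itself avoid residual N-13 activity; with no correction described, rest MBF would read high and MPR low

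*Combined protocol and SAP*

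**What the plan says.** All places are in the Combined protocol and SAP.

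- **Section V, Stress PET.** Stress is imaged first: "10-12 mCi N-13 ammonia will be hand injected as a bolus". Its acquisition start is explicit: "PET emission scan in list mode will be started scan exactly with or seconds before N-13 ammonia injection". Its duration is not given.
- **Section V, Rest PET.** The gap and its reason are: "Approximately 30-40 minutes later, to allow sufficient decay of N-13 ammonia to avoid residual activity in the heart, we will perform the rest imaging". The event from which the gap is counted is not stated. Before the rest injection, "A repeat non-contrast AC CT scan will be obtained and the rest PET N-13 ammonia perfusion imaging will be performed". The rest acquisition is worded as following an injection of about "10-12 mCi of N-13 ammonia, PET acquisition over 10 minutes in list mode will be conducted".
- **Section VI, Image Analysis.** PET quantification is one sentence: "Segmental MBF at stress and rest, and MPR will be calculated using QPET, Cedar-Sinai software". It mentions no residual correction, pre-injection frame or software settings.
- **Sections II, IV and VII.** Segmental MBF and MPR form the secondary endpoint, analysed by Pearson correlation with Spearman as the alternative. PET MBF/MPR alone, and a hybrid that includes MPR, are also compared with ICA/FFR. No MPR or MBF cut-off is given.

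**The concern.** The plan gives one safeguard against carry-over from the stress injection, which is decay during the gap, and puts no figure on it. N-13 decays quickly, but 30-40 min is only three to four half-lives. Two features leave the rest scan exposed: the scan with the higher myocardial uptake comes first, and the second injection is not larger than the first by design.

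Activity already in the myocardium when the rest bolus arrives can be read as rest uptake. Rest MBF is then too high and MPR, its quotient with stress MBF, too low. The size would vary between patients with the actual gap and the ratio of the two injected activities. At stake are the absolute rest MBF and MPR values this pilot reports, and any MPR threshold later applied in the PET-alone or hybrid comparison.

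**Working it through.** The plan states no residual figure, so there is none to reproduce.

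**Inputs from the document.** Gap about 30-40 min; stress and rest activity 10-12 mCi each; rest acquisition 10 min.

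**Assumptions.** N-13 half-life 9.965 min (10.0 as a check); stress scan 10 min for the second reading of the clock; kinetic parameters as in step 3.

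**Step 1. Fraction remaining**, f(t) = 2^(−t/9.965), where t is the time from stress injection to rest injection:

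| t (min) | Equal doses | Stress 10, rest 12 mCi (× 10/12) | Stress 12, rest 10 mCi (× 12/10) |
|---|---|---|---|
| 30 | 12.4% | 10.3% | 14.9% |
| 35 | 8.8% | 7.3% | 10.5% |
| 40 | 6.2% | 5.2% | 7.4% |
| 50 | 3.1% | 2.6% | 3.7% |

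A half-life of 10.0 min gives 12.5%, 8.8%, 6.3% and 3.1% at equal doses. If the gap is counted from stress injection, t is 30-40 min and 6.2-12.4% remains. If it is counted from the end of a 10-min stress scan, t is 40-50 min and 3.1-6.2% remains. Time taken by the repeat attenuation CT, if not already inside the gap, would lower these a little further.

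**Step 2. Does the assumed half-life decide the matter?** For only 1% to remain, the half-life would have to be 30/log2(100) = 4.5 min at 30 min, or 40/log2(100) = 6.0 min at 40 min.

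**Step 3. From residue to MBF and MPR.** The remaining fraction is not itself the bias in flow. An illustrative compartment model was used with an assumed input function and rate constants, and true rest MBF 0.8. The residue was added to the decay-corrected rest curve as a constant (no biological washout), and the first 4 min were fitted with no residual term. If rest MBF is inflated by a fraction b, observed MPR = true MPR/(1 + b):

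| t (min) | b, true MPR 1.5 | Reads | b, true MPR 2.5 | Reads | b, true MPR 3.5 | Reads |
|---|---|---|---|---|---|---|
| 30 | 21.1% | 1.24 | 24.6% | 2.01 | 26.5% | 2.77 |
| 40 | 10.4% | 1.36 | 12.1% | 2.23 | 13.0% | 3.10 |
| 50 | 5.2% | 1.43 | 6.0% | 2.36 | 6.5% | 3.29 |

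MPR is therefore low by 5-6% at 50 min, 9-12% at 40 min and 17-21% at 30 min. Fitting all 10 min gives slightly larger inflation, up to 28.7%. A second simulation with other assumed kinetics gave less: a true 2.5 read 2.18 at 30 min and 2.33 at 40 min (13% and 7% low), and a true 1.5 read 1.32 and 1.41. With no residue in the rest curve, which is what exact subtraction would leave, the fit returned 0.80.

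**Step 4. Effect on the planned correlations.** Assume MPR with mean 2.0 and SD 0.4 or 0.6, and a gap uniform over 30-40 min from stress injection. Take rest inflation at 30 min as either 15% or the step 3 values, scaled by f(t). A true Pearson correlation of 0.45 becomes about 0.44-0.45, and 0.70 becomes about 0.69-0.70. Letting both doses vary over 10-12 mCi leaves those ranges unchanged, and Spearman's coefficient falls by similarly small amounts. For scale, the approximate standard error of r = 0.45 at n = 35 is (1 − 0.45²)/√32 = 0.14.

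**The case against.** The strongest case on the other side has four parts.

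1. **The planned statistic is barely touched.** In the second simulation above, 2.5 becomes 2.18 (× 0.87) and 1.5 becomes 1.32 (× 0.88) at 30 min. This is nearly uniform rescaling, which leaves Pearson and Spearman coefficients unchanged, and gap-to-gap variation adds little. This stands. A reader might infer from the smaller absolute difference between normal and stenotic territories that discrimination is lost. The figures do not support that, because the whole scale shrinks together.
2. **Silence is not absence.** Section VI does not say how the software is configured, so correction cannot be ruled out. This stands. A reader might infer that MPR in this trial is biased; the documents support only that it would be if the residue is left uncorrected.
3. **The clock is undefined.** The 6-12% figure takes the less favourable reading, and 3-6% is equally consistent with the text. This stands, but neither reading delivers the property the protocol claims.
4. **No cut-off is prespecified, and the sizes depend on assumed kinetics.** Both are true. No defined classification is shown to be wrong, and the MPR figures give direction and order of magnitude only. However, comparing PET alone or the hybrid with ICA/FFR will need some rule for using MPR, and an absolute shift would then count. A segment with true MPR 2.5 that reads 2.01 changes side for any cut-off between those values.

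The objection does not rescue the stated rationale. Nor does it explain why the rest acquisition, the only one with a residue to measure, is worded as following injection while the stress acquisition starts at or just before it.

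**Conclusion.** The point holds in limited form. The interval does not avoid residual activity: about 6-12% of the stress activity remains on one reading of the clock and 3-6% on the other, given a half-life near 10 min and nominally equal doses. This part is firm.

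If the residue is not corrected, rest MBF would be biased up and MPR down by very roughly 5-20%. Rest MBF inflation reaches the high twenties per cent at 30 min under the less favourable kinetics. These sizes rest on assumed kinetics and no washout.

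What is exposed is absolute rest MBF, absolute MPR, and any MPR cut-off used for PET alone or the hybrid. The correlations are little affected. A reader might infer that the main result is compromised. It is not: the primary endpoint is CT-FFR, which does not use PET, and stress MBF is measured before any residue exists. The change is worth making because it is cheap and because a pre-injection frame cannot be recovered after the scan.

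**What to change.** Leave the interval and both doses as they are.

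- **Acquisition.** Start the rest list-mode acquisition shortly before the rest injection, for example 30-60 s, so that it contains a pre-injection frame.
- **Analysis.** In section VI, state that residual myocardial and blood-pool activity is measured in that frame and subtracted, decay-corrected, from the rest frames before rest MBF and MPR are calculated. Alternatively, confirm that the software's own residual correction is switched on and say what it needs from the acquisition.
- **Recording.** Record both injection times and both assayed activities for every patient, and define the event from which the interval is counted.
- **Text.** Delete the claim that the interval alone avoids residual activity.

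The cost is under a minute of extra list-mode time, one analysis step and slightly more noise in rest MBF. There is no added radiation or procedure. If the software already corrects for the residue, the change is a sentence in section VI, the acquisition start and the recorded times and activities.

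### The unit of analysis for the PET correlations is undefined: the endpoint is segmental, the named methods assume independent pairs, and nothing handles several values per patient

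*Combined protocol and SAP*

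**What the plan says.** Sections II and VII give the same secondary endpoint: "Our secondary endpoint will be the correlation of segmental PET MBF and MPR to presence or absence of a coronary artery stenosis" of at least 50% diameter and, in patients with such a stenosis, "correlation with CT-cFFR, and ICA/ICA FFR for which we will perform a Pearson correlation coefficient". The only alternative is conditional on non-linearity: "Spearman's rank correlation coefficient may be used as an alternative if there are issues with the assumption of a linear model".

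Section VI sets the level of the PET measurement: "Segmental MBF at stress and rest, and MPR will be calculated using QPET". The same section calculates CT-FFR only for lesions with at least 50% stenosis, so that comparator belongs to a lesion. Section VII takes the invasive FFR reference per epicardial artery. A further comparison names no method: "CAC in each epicardial artery will be compared to regional MBF".

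The sample size paragraph of Section VII says that "a sample size of 35 achieves 80% power to detect a correlation of 0.45 using a two-sided Pearson correlation" "with a significance level of 0.05". The 35 are patients (Section IV: "Thirty-five patients presenting with stable angina and a moderate pretest likelihood for CAD").

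The documents give no number of segments per heart, no mapping of segments to arteries, no rule for reducing segments to one value per artery or patient, and no method for repeated values within a patient.

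**The concern.** Each heart yields several MBF and MPR values, and segments supplied by one artery share one stenosis or FFR value. Segments of one heart also share the microvasculature, the haemodynamic state, the tracer injection and the input function. The pairs are therefore not independent, which the usual Pearson and Spearman tests and intervals require. Moving from Pearson to Spearman deals with non-linearity and leaves this untouched.

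The power statement counts one pair per patient and the endpoint counts segments, so the two describe different analyses. An analyst who follows Section VII literally would correlate segment values with artery values and could report chance associations as significant. These correlations address the comparison named in the study title, although they are secondary in the analysis plan.

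**Working it through.** **1. The plan's power figure.** Inputs from Section VII: r = 0.45, n = 35, two-sided 0.05. Fisher z with bias term: power = Φ[(atanh r + r/(2(n−1)))·√(n−3) − 1.96] = Φ[(0.4847 + 0.0066)×5.657 − 1.96] = Φ(0.819) = 79.4%. A bivariate-normal simulation also gives 79.4%. The stated 80% therefore reproduces for 35 independent pairs, one per patient.

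**2. What pooling would do to the printed interval.** At r = 0.45 the 95% interval is tanh(0.4847 ± 1.96/√(n−3)).
- 35 pairs: tanh(0.4847 ± 0.3465) = (0.14, 0.68).
- 35 × 17 = 595 pairs: tanh(0.4847 ± 0.0806) = (0.38, 0.51).

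**3. Error of the pooled test, segment level.** The documents give no segment count or intraclass correlation, so these are assumptions: 17 segments split 7/5/5 over three arteries; a share p of MPR variance between patients and t between territories; one comparator value per artery, with a share c of its variance between patients. With no true association, the variance of r is inflated by the average, over segments, of the summed products of the two within-patient correlations.
- Ordered pairs of different segments in one territory: 7×6 + 5×4 + 5×4 = 82. Product: 1 × (p + t).
- Ordered pairs in different territories: 17×16 − 82 = 190. Product: c × p.
- D = 1 + (82/17)(p + t) + (190/17)·c·p. Actual error = 2[1 − Φ(1.96/√D)].

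| p, t, c | D | SE understated by √D | 595/D | Actual error |
|---|---|---|---|---|
| 0.30, 0.15, 0.20 | 1 + 2.171 + 0.671 = 3.84 | 1.96 | 155 | 32% |
| 0.60, 0.20, 0.50 | 1 + 3.859 + 3.353 = 8.21 | 2.87 | 72 | 49% |
| 0.30, 0.15, 0 | 1 + 2.171 = 3.17 | 1.78 | 188 | 27% |
| 0.60, 0.20, 0 | 1 + 3.859 = 4.86 | 2.20 | 122 | 37% |

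Simulation agrees: 31–50% when the comparator clusters within patients and 26–38% when it does not. The error stays high at c = 0 because segments still share their artery's value.

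**4. One mean per artery territory.** The intraclass correlation of the means is about p/[p + t + (1 − p − t)/(17/3)], and D = 1 + 2 × that × c.
- p = 0.30, t = 0.15, c = 0.20: 0.300/0.547 = 0.55; D = 1.22; error 8%.
- p = 0.60, t = 0.20, c = 0.50: 0.600/0.835 = 0.72; D = 1.72; error 13–14%.
- c = 0: D = 1; error 5%.
- Exactly one diseased artery per patient: the comparator's within-patient correlation is −0.5, so D = 1 − (intraclass correlation of MPR). At 0.3 and 0.7 simulation gives about 2% and 0.1%, which is conservative.

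Simulations over the assumed range gave 6–14%. An extreme case, with the same comparator value in all three arteries of a patient and an MPR correlation of 0.7, gave 21%.

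**5. The FFR correlations.** They use only patients with at least 50% stenosis, and CT-FFR exists only for such lesions, so 595 pairs cannot arise there. Simulation with diseased arteries only (assumed 60/30/10% with one, two or three; 15–25 patients) gave 5–9% per artery and about 28–45% per segment. At one pair per patient, the formula in step 1 gives power for r = 0.45 of 53% with 20 patients and 41% with 15 (assumed subset sizes).

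**The case against.** The strongest reply is that the plan never says segments will be pooled. Its only correlation calculation fits one pair per patient. The word segmental in Section VI describes software output, and elsewhere the document speaks of regional flow, so a reading by artery territory is natural. At that level the error is small to modest and can reverse. This stands: a reader might infer that the plan treats every segment as an independent pair and that its results will be far too optimistic, but the documents show only that the unit is undefined.

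It also stands that the segment count, the 7/5/5 split and all variance shares are assumptions, that the 595-pair count cannot apply to CT-FFR, and that the plan promises no interval for the correlations. The sentence structure may attach Pearson only to the FFR correlations, which leaves the yes/no stenosis comparison without a stated method. That is a further gap and no defence.

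This is a pilot whose primary aim is diagnostic accuracy, and nothing in the documents makes a treatment decision depend on these p-values.

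The reply does not supply a reduction rule. If one value per patient was intended, the plan does not say how it is chosen, and the endpoint is then no longer segmental.

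**Conclusion.** The concern holds in conditional form. The endpoint is segmental, the comparators are per artery or lesion, the named methods need independent pairs, and no method for within-patient correlation is given. If segments enter as separate pairs, a nominal 5% test would reject in roughly 26–50% of null trials under the assumptions in step 3. With territory means the figure is about 5–14%, and it can fall below 5%. The harm therefore depends mainly on a choice that the plan leaves open. Confidence is high that the method is missing; the size of the effect rests on undocumented inputs. The change should be made before analysis.

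**What to change.** In Section VII:

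- Name the patient as the independent unit. State the segment-to-artery mapping and average segments to the artery territory.
- Estimate each association with a linear mixed model with a random patient intercept: the mean MBF/MPR difference for stenosis yes/no, and the slope for CT-FFR and for invasive FFR. Alternatively, report the correlation with a 95% interval and p-value from a bootstrap that resamples whole patients. In the one setting tried (35 patients, three territories, 400 trials) the bootstrap's error was about 7%, so it is approximate at this size.
- State the method for the yes/no stenosis comparison explicitly, and use the same approach for CAC against regional MBF.
- State that 80% power for r = 0.45 applies to 35 independent pairs, one per patient, and not to a segmental analysis or to the smaller subset with at least 50% stenosis.

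The cost is SAP wording and a few lines of code. The downside is wider, less favourable intervals.
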